9.7.1.6.3 EXPLORATORY EFFICACY ANALYSES

(revised per Amendments 01, 02, 04, and 05)

An MMRM will be used to analyze the following exploratory endpoints:

- Change from baseline in CSF A β (1-40) and BACE1 variables (eg, activity and protein levels) from 4 weeks and up to 18 months. Data from early discontinuations will also be included. (revised per Amendment 04)
- Change from baseline in CSF biomarkers of neurodegeneration (eg, t-tau and p-tau) at 18 months of treatment
- Change from baseline in plasma amyloid measurements from 4 weeks and up to 18 months of treatment, and during post-treatment follow-up
- Change from baseline in CSF amyloid and CSF BACE1 measurements from 4 weeks and up to 18 months of treatment (revised per Amendment 06)
- Change from baseline in total hippocampal atrophy at 12 and 18 months as measured by vMRI
- Change from baseline in left and right hippocampal, whole brain, and total ventricular volume at 6, 12 and 18 months as measured by vMRI
- Change from baseline in Amyloid PET SUVR composite at 18 months for brain amyloid levels

The following efficacy endpoints will be summarized using descriptive statistics:

- Change from baseline in the clinical assessments: ADAS-cog₁₄, CDR, MMSE, ISLT, CBB, and FAQ at 12 weeks and at 6, 9, 12, 15, 18, 19, and 21 months

The relationship between efficacy endpoints and biomarker endpoints will be explored using correlation analysis.

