9.5.1.5.7 SAFETY MRI

Safety brain MRI assessments will be performed at the times shown in [Table 6](#) and [Table 7](#). Additional safety MRI scans can be performed at unscheduled visits if clinically necessary. MRI acquisition and interpretation will be organized centrally to ensure reproducibility and consistency between units involved.

Safety MRIs will be acquired using a standardized procedure that will include fluid-attenuated inversion recovery (FLAIR), gradient-echo, T1, and diffusion-weighted sequences to determine the presence of focal lesions including, but not limited to, evidence for ischemic and hemorrhagic stroke, subdural hematoma, neoplasm, arteriovenous malformation, micro and macrohemorrhages, superficial siderosis, lacunar infarcts, white matter abnormalities, and vasogenic edema. The imaging sequence for the Screening/safety MRI will include: T2 weighted anatomic MRI to rule out major white matter changes, cerebral infarction or other structural lesions, and a high-resolution 3D T1-weighted scan with isotropic voxels with volumes of 1 mm³ or less. In addition, both FLAIR for the detection of vasogenic edema and T2 Gradient Recall Echo for the detection of microhemorrhages will be acquired. The 3D dataset will be reconstructed in transverse slices in Digital Imaging and Communications in Medicine format. The results of this MRI assessment will also be used as the Baseline Period MRI, against which changes after drug administration will be compared. Further details of the MRI protocol can be found in the Imaging Acquisition Guideline. MRI acquisition and interpretation will be organized centrally to ensure reproducibility and consistency between units involved. MRI imaging will be conducted on separate days from the scheduled visits. MRI imaging should be conducted within the 7 days before Visits 14, 16, and 18 and at the final Follow-Up Visit (Visit 20). (revised per Amendment 04) In the event of an Unscheduled Visit, the investigator in consultation with the sponsor will determine whether or not a safety MRI should be conducted. If an ED Visit takes place, an MRI is to be conducted if not already performed during the preceding 90 days.

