- q: Safety MRIs will be acquired using a standardized procedure that will include gradient echo, long tau inversion recovery, and diffusion-weighted imaging sequence images in MRI will be read by an approved central reader. MRI imaging will be conducted on separate days from the scheduled visits. MRI imaging should be conducted within the 7 days before Visits 14, 16, 18, and 20. In the event of an Unscheduled Visit, the investigator in consultation with the sponsor will determine whether or not a safety MRI should be conducted. If an ED Visit takes place, an MRI is to be conducted if not already performed during the preceding 90 days. A volumetric MRI sequence will be collected in all subjects immediately following all safety MRI assessments. (revised per Amendment 01)
- r: PET scanning will be performed with a locally approved amyloid β imaging agent, eg, Amyvid, if available or an agent under clinical investigation if no agents are approved locally; the imaging agent must remain unchanged for an individual subject throughout the study. A PET scan will only be performed at an ED Visit if the subject has been treated with study drug for at least 39 weeks. A PET scan will only be performed at Visit 18 or ED if the subject has a valid Screening PET scan for the purposes of longitudinal analyses; subjects who were determined to be eligible for the study on the basis of an historical PET scan will not have a PET scan performed at Visit 18 or ED (revised per Amendment 02)
- s: Site staff will contact the subject or the caregiver or informant the day before the PK blood sampling to provide instructions that subjects must not take their study drug at home on the day of the PK blood sampling. During this telephone contact with the subject or the caregiver or informant, the site staff should document the time that the subject took their study drug that day, ie, the day before the PK blood sampling.

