9.7.1.1.3 EXPLORATORY ENDPOINTS

(revised per Amendments 01, 02, 04, and 05)

Change from baseline in:

- CSF A β (1-40) and BACE1 variables (eg, activity and protein levels) after at least 4 weeks and at 18 months of treatment
- CSF biomarkers of neurodegeneration (eg, t-tau and p-tau) at 18 months of treatment
- Plasma amyloid measurements from 4 weeks and up to 18 months of treatment, and during posttreatment follow-up
- CSF amyloid and CSF BACE1 measurements after 4 weeks and 18 months of treatment (revised per Amendment 06)
- Total hippocampal volume at 12 and 18 months of treatment as measured by vMRI
- Left and right hippocampal, whole brain, and total ventricular volume at 6, 12, and 18 months of treatment as measured by vMRI
- Amyloid PET standardized uptake value ratio (SUVR) composite at 18 months for brain amyloid levels as measured
- The following clinical assessments at 12 weeks and at 6, 9, 12, 15, 18, 19, and 21 months: ADAS-cog₁₄, CDR, MMSE, ISLT, CBB, and FAQ

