9.5.1.3.2 VOLUMETRIC MRI

Volumetric MRI will be used to evaluate disease modification as indicated by measurements of brain atrophy, including the change from Baseline in terms of the measured hippocampal volume based upon the centralized measurement of the structure on repeated MRIs. A large number of studies, including the Alzheimer's Disease Neuroimaging Initiative, have shown that quantitative measurements of hippocampal, whole brain, and total ventricular volume provide robust and reliable biomarkers of disease progression, and potential for assessment of PD efficacy.

Volumetric MRI sequences will be collected for all subjects immediately following all safety MRI scans in the same imaging session. Volumetric MRI will be conducted at either 1.5T or 3T, and across multiple scanner types and the type of scanner used will be documented. Volumetric MRI analysis will be performed by a central imaging laboratory on MRI scans obtained at the times specified in [Table 6](#) and [Table 7](#), according to standard quality control and normalization procedures for measurements of the whole brain and total ventricular volume. Measurements of the right and left hippocampal volumes will be based on a validated algorithm and conducted in the same laboratory. Additional analysis of regions of interest and cortical thickness may also be performed.

Descriptions and detailed instructions for all imaging can be found in the imaging manual.

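### Total hippocampal volume enters the MMRM at months 12 and 18 only, although the same scans give a month-6 value that could be modelled at no cost

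*Protocol*

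**What the plan says.** Section 9.7.1.6.3 opens its list with "An MMRM will be used to analyze the following exploratory endpoints". Two items in that list concern the hippocampus:

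- Total: "Change from baseline in total hippocampal atrophy at 12 and 18 months as measured by vMRI".
- Parts: "Change from baseline in left and right hippocampal, whole brain, and total ventricular volume at 6, 12 and 18 months as measured by vMRI".

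Section 9.7.1.1.3 makes the same split, giving the total as "Total hippocampal volume at 12 and 18 months of treatment as measured by vMRI". The exploratory objectives in Section 8.3 and the synopsis repeat it.

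The month-6 scan is scheduled and includes the volumetric sequence. Footnote q of Table 7 says "MRI imaging should be conducted within the 7 days before Visits 14, 16, 18, and 20" and "A volumetric MRI sequence will be collected in all subjects immediately following all safety MRI assessments". Visits 14, 16 and 18 are nominal months 6, 12 and 18. Section 9.5.1.3.2 adds "Measurements of the right and left hippocampal volumes will be based on a validated algorithm and conducted in the same laboratory".

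No reason is given for leaving month 6 out of the total alone. Section 9.2.4.4 in fact supports volumetric analysis at six-month intervals.

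**The concern.** An MMRM uses whatever post-baseline values are placed in its response vector. Its missing-at-random protection covers dropout that can be predicted from data inside the model. If months 12 and 18 are the only response visits for the total, two things follow:

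- A subject with a month-6 scan and no later usable scan contributes nothing to the total. That subject still belongs to the PD Analysis Set (Section 9.7.1.2) and still contributes to the left and right analyses.
- If subjects with more atrophy at month 6 are more likely to stop, the model cannot see the value that predicts their leaving.

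With about 15 subjects per arm and no replacement of those removed (Section 9.5.5), each lost subject counts. Section 9.2.4.4 looks to hippocampal atrophy for support of disease modification. The protocol expects the study to inform the Phase 3 decision, so the measure is worth analysing efficiently.

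**Working it through.** The protocol gives no effect size, SD, power or dropout rate for volumetric MRI, so there is no planned figure to reproduce. From the documents come 15 per arm (60/4), the scan visits and the two-sided 5% level. Everything else below is an assumption, shown as a range.

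**1. Is the month-6 total available?** Yes. Left and right are measured at month 6 by one method in one laboratory, so total = left + right. No new scan or reading is needed.

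**2. Precision.** A simulation compared month-18 estimates from an unstructured-covariance likelihood fit (equivalent to MMRM under monotone missingness) with and without month 6. Inputs:
- 15 per arm and a true month-18 difference of 0.5 SD.
- Between-visit correlation of 0.5 or 0.8.
- 10%, 20% or 30% lost between months 6 and 12, and 10% of the rest before month 18.

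Results at 15 per arm:

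| Correlation | SE without month 6 / SE with month 6 |
|---|---|
| 0.5 | 1.01 to 1.04 |
| 0.8 | 1.03 to 1.12 |

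The largest ratio is at 30% random loss and correlation 0.8: 0.459/0.410 = 1.12. In that case 21 of 30 subjects inform the model without month 6, and all 30 inform it with month 6.

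**3. Bias.** This depends on the dropout mechanism.
- Random dropout: none.
- Dropout depending on month 6 by the same rule in both arms, in the simulation above: within ±0.025 SD. Against a true 0.5 SD that is at most 0.025/0.5 = 5%.
- Dropout depending on month 6 by the same rule in both arms, but with linear atrophy and random slopes: the month-18 difference shrinks by about 1% to 15%, and adding month 6 removes this. The inputs were of the following kind: placebo loss 3% per year, 30% to 50% slowing, slope SD 1 to 2% per year, measurement SD 0.7%, and roughly 20% to 40% or more lost after month 6. Shrinkage arises because a real treatment effect already separates the arms at month 6, so a common rule removes more fast decliners from placebo. A steep dropout link gave up to 24%, but nothing in the protocol supports choosing one.
- Dropout depending on month 6 in the active arm only: a shift of +0.04 to +0.23 SD, so the direction can reverse. With month 6 added it is about zero.

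**4. Size against the noise.** Take 30% slowing and slope SD 1.5. The true difference is 1.354 percentage points, against 1.189 without month 6 and 1.351 with it.
- Bias = 1.354 − 1.189 = 0.165, and 0.165/1.354 = 12%.
- Month-18 SD = √[(1.5 × 1.5)² + 0.7²] = √5.55 = 2.36.
- SE at 15 per arm with no dropout = 2.36 × √(2/15) = 0.86.
- Bias/SE = 0.165/0.86 ≈ 0.2.

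For context, 15 per arm detects (1.96 + 0.84) × √(2/15) ≈ 1.02 SD with 80% power.

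**The case against.** The strongest reply is that these items name endpoint time points and do not define the model's response visits. Section 9.7.1 leaves further detail to the SAP, which could model months 6, 12 and 18 and report months 12 and 18 without contradicting the protocol. That is fair, and it limits the point. But the protocol is not silent: under one MMRM sentence it gives the total two visits and its parts three. A SAP author following the text would leave month 6 out.

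Four stronger readings are tempting, and the documents do not support them.

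- **That the estimate is biased.** No dropout rate or mechanism is given. The discontinuation criteria in Section 9.3.3 concern lymphocytes, infection, rash, MRI lesions, QTcF, seizure and pregnancy; none is atrophy. Bias is possible, not established.
- **That early discontinuers are excluded by design.** Only subjects without a usable month-12 or later scan are affected. Section 9.5.1.5.7 says "If an ED Visit takes place, an MRI is to be conducted if not already performed during the preceding 90 days", and Visit 20, 12 weeks after the last dose, includes an MRI. The use of these scans in the volumetric model is neither stated nor barred.
- **That Amendment 05 removed relevant scans.** The post-discontinuation visits it dropped carried clinical scales only, as the preceding version's synopsis shows.
- **That adding month 6 makes the total effect equal left plus right.** Separately fitted MMRMs with missing data generally do not add up, even with identical visits.

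Nor is total hippocampal volume named as the leading imaging measure. Section 9.2.4.1 lists volumetric MRI beside amyloid PET and CSF tau, and Section 9.7.1.6.1 states that there is no primary efficacy endpoint.

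**Conclusion.** The point holds as a low-severity improvement. The text leaves an available month-6 value out of the total hippocampal analysis while using it for both halves, without a stated reason. The precision loss is small and conditional on the assumed correlations and dropout. Shrinkage of the month-18 difference is a further possibility that needs dropout linked to month-6 atrophy. In the worked example it is about one fifth of a standard error, so it would not by itself change a conclusion from 15 per arm. The case for acting rests on the change costing nothing.

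**What to change.** In Section 9.7.1.6.3, and in the matching synopsis text, state that total hippocampal volume (left plus right) enters the MMRM at months 6, 12 and 18 as response visits. Keep months 12 and 18 as the time points at which the treatment difference is reported; the endpoint wording in Section 9.7.1.1.3 can then stay, read as reporting times. The cost is wording only, with no added scan, visit or reading. How ED and Visit 20 scans are handled can be left to the SAP.

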9.7.1.7 Pharmacokinetic, Pharmacodynamic, Pharmacogenomic, and Other Biomarker Analyses

9.7.1.7.1 PHARMACOKINETIC ANALYSES

The PK Analysis Set will be used for E2609 concentration listings and for summaries of E2609 concentrations in plasma and CSF by dose and day. E2609 metabolite PK data may also be listed and summarized. (revised per Amendment 04)

A population PK approach will be used to characterize the plasma PK of E2609. For this approach, plasma PK data from this study will be pooled with relevant data from Phase 1 studies. As appropriate, the effect of covariates on the PK of E2609 will be evaluated. The PK model will be parameterized for oral clearance (CL/F) and apparent volume of distribution (V_z/F) for E2609. Derived exposure parameters such as steady state area under the concentration time curve (AUC) and average concentration (C_{avg}) of E2609 and other derived parameters will be calculated from the model using the individual estimates parameterized for oral clearance and dosing history. (revised per Amendment 04)

9.7.1.7.2 PHARMACODYNAMIC, PHARMACOGENOMIC, AND OTHER BIOMARKER ANALYSES

Pharmacodynamic, PGx, and other biomarker analyses may be performed and reported separately. Details of these analyses may be described in a separate statistical analysis plan. Please also refer to [Appendix 3](#).

Pharmacodynamic Analyses

The PD Analysis Set will be used for the summaries and analyses of PD biomarkers (CSF and plasma biomarkers, MRI endpoints). The percentage change from baseline in CSF A β (1-x), A β (1-42), A β (1-40), t-tau, p-tau, and BACE1 variables (eg, activity and protein levels) from 4 weeks and up to 18 months of treatment will be analyzed and presented graphically. (revised per Amendment 05) Baseline levels and changes in t-tau and p-tau will be correlated with changes in CSF A β (1-42), imaging markers, and *ApoE4* status. (revised per Amendment 04)

Summary statistics for CSF biomarkers will be assessed for evidence of a dose relationship.

Pharmacokinetic and Pharmacodynamic Analyses

The PK/PD relationship between CSF biomarker levels, amyloid load on PET, vMRI, and E2609 dose, plasma, and CSF exposure will be initially explored graphically and any emergent relationship will be explored through population PK/PD modeling. The PK/PD relationship between plasma PK parameters with other biomarkers may also be explored using similar methods. (revised per Amendment 04)

The relationship between plasma and CSF exposure to E2609 and the clinical efficacy scales (eg, MMSE, CDR) will be explored graphically. Additionally, the relationship between plasma exposures of E2609 and select lymphocyte parameters will be explored graphically, and any emergent relationship will be explored using population-based modeling methods. (revised per Amendment 04)

Exposure-safety analyses may also be conducted.

Pharmacogenomic Analyses

Blood samples will be used to determine the *ApoE* genotype and the *NAT2* phenotype of subjects enrolled in this study. The genomic DNA samples may also be stored and used as described in [Section 9.7.1.7.2](#). Details of PGx testing may be provided and reported separately.

9.7.1.8 Safety Analyses

Evaluations of safety will be performed on the Safety Analysis Set. The incidence of AEs (including changes from baseline in physical and neurological examinations, and dermatological assessments), out-of-normal-range laboratory safety test variables, abnormal ECG findings, out-of-range vital signs, suicidality (C-SSRS), and results of the sleep questionnaire, along with the change from baseline in laboratory safety test variables, ECGs, safety MRI, vital sign measurements, and cognitive decline assessment such as CBB will be summarized by treatment group using descriptive statistics. (revised per Amendment 05)

9.7.1.8.1 EXTENT OF EXPOSURE

The extent of exposure to study drug will be summarized as cumulative extent of exposure in 3-month intervals. The cumulative number and percent of subjects will be presented by treatment group. Duration of exposure will be summarized using descriptive statistics as continuous variable as well as categorical variable in 3-month intervals and the number and percent of subjects will be presented by treatment group.

9.7.1.8.2 ADVERSE EVENTS

The AE verbatim descriptions (investigator terms from the eCRF) will be classified into standardized medical terminology using the Medical Dictionary for Regulatory Activities

(MedDRA). Adverse events will be coded to the MedDRA (Version 17.0 or higher) lower level term closest to the verbatim term. The linked MedDRA preferred term and primary system organ class (SOC) are also captured in the database.

A TEAE is defined as an AE that emerges during treatment, having been absent at pretreatment (Baseline) or

- Reemerges during treatment, having been present at pretreatment (Baseline) but stopped before treatment, or
- Worsens in severity during treatment relative to the pretreatment state, when the AE is continuous.

Only those AEs that are treatment-emergent will be included in summary tables. All AEs, treatment-emergent or otherwise, will be presented in subject data listings.

The TEAEs will be summarized by treatment group on the Safety Analysis Set. The incidence of TEAEs will be reported as the number (percentage) of subjects with TEAEs by SOC and preferred term. A subject will be counted only once within an SOC and preferred term, even if the subject experienced more than 1 TEAE within a specific SOC and preferred term. The number (percentage) of subjects with TEAEs will also be summarized by maximum severity (mild, moderate, or severe). The number (percentage) of subjects with TEAEs will also be summarized by relationship to study drug (Yes [related] and No [not related]).

The number (percentage) of subjects with treatment-related TEAEs will be summarized by SOC and preferred term. Treatment-related TEAEs include those events considered by the investigator to be related to study drug. The number (percentage) of subjects with treatment-related TEAEs will also be summarized by maximum severity (mild, moderate, or severe).

Adverse events will be summarized by the following subgroups: *ApoE4* status (positive or negative), prior treatment with AChEIs or memantine (no or yes), and clinical population (MCI/Prodromal or mild to moderate AD). (revised per Amendment 01)

The number (percentage) of subjects with TEAEs leading to death will be summarized by MedDRA SOC and preferred term for each treatment group. A subject data listing of all AEs leading to death will be provided.

The number (percentage) of subjects with treatment-emergent SAEs will be summarized by MedDRA SOC and preferred term for each treatment group. A subject data listing of all SAEs will be provided.

The number (percentage) of subjects with TEAEs leading to discontinuation from study drug will be summarized by MedDRA SOC and preferred term for each treatment group. A subject data listing of all AEs leading to discontinuation from study drug will be provided.

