[Part 3 of 7 of the document. The other parts are not shown.]

An AE is any untoward medical occurrence in a subject or clinical investigation subject administered an investigational product. An AE does not necessarily have a causal relationship with the medicinal product. For this study, the study drug is E2609.

The criteria for identifying AEs in this study are:

- Any unfavorable and unintended sign (including an abnormal laboratory finding), symptom, or disease temporally associated with the use of an investigational product,

whether or not considered related to the investigational product (Note: It is not necessary to report every sign or symptom as a separate AE if the overall disease [diagnosis] is being reported as an AE.)

- Any new disease or exacerbation of an existing disease
- Any deterioration in nonprotocol-required measurements of a laboratory value or other clinical test (eg, ECG or x-ray) that results in symptoms, a change in treatment, or discontinuation of study drug
- Recurrence of an intermittent medical condition (eg, headache) not present pretreatment (Baseline)
- An abnormal laboratory test result should be considered an AE if the identified laboratory abnormality leads to any type of intervention, discontinuation of study drug, or withholding of study drug, whether prescribed in the protocol or not

All AEs observed during the study will be reported on the eCRF. All AEs, regardless of relationship to study drug or procedure, should be collected beginning from the time the subject signs the study ICF through the last visit (Visit 20, as shown in [Table 7](#)). Subjects who fail screening primarily due to AE(s) must have the AE(s) leading to screen failure reported on the Screening Disposition eCRF. SAEs will be collected for 3 months after the last dose of study drug, ie, through to the final Follow-Up visit (Visit 20). However, any SAEs volunteered by subjects after this time point must be reported according to standard procedures. (revised per Amendments 04 and 05)

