9.7.1.1 Study Endpoints

9.7.1.1.1 PRIMARY ENDPOINT

- Safety and tolerability, which include incidence of TEAEs and SAEs, laboratory parameters, vital signs, and ECG parameters (revised per Amendment 05)

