In the MAD study, AEs of interest included relapse of orolabial herpes, viral respiratory tract infection, drug rash, and abnormal dreams. More details are available in the Investigator's Brochure. In summary, E2609 administered at doses of 200 and 400 mg was associated with reductions in CD4 (T helper cells), CD8 (cytotoxic T cells), and CD19 (B cells) counts at Day 8. These reductions were more clearly evident by Day 15, consistent with a treatment by time interaction in the statistical analysis. There was evidence that the lower doses of 50 to 100 mg also caused some reduction in CD4 lymphocyte counts by Day 15. Doses above 100 mg appeared to be associated with greater reductions in CD4 and CD8 lymphocyte counts, which occurred earlier in the treatment period compared with the effects of 25 to 100 mg doses. These effects on lymphocyte counts gradually resolved from Day 20 to Day 35, which were 6 and 21 days, respectively, after administration of the last dose of E2609 on Day 14. Reductions in CD4 and CD8 lymphocyte counts at doses of 200 and 400 mg to a level close to or less than the lower limit of normal (LLN) could be associated with increased risk of developing relapse of orolabial herpes or other infections.

In Study 003, a drug-drug interaction study, PK results showed that itraconazole (a potent inhibitor of cytochrome P450 [CYP3A4] and carboxyesterase-2 [CES2]) increased by

approximately 70% the area under the concentration \times time curve (AUC) of E2609. Consequently, strong inhibitors of CYP3A4 will be prohibited in this study.

Rifampin (a potent CYP3A4 inducer) caused a mild decrease (by approximately 20%) of the AUC of E2609. Therefore, no restrictions are required for the use of concomitant medications which are known to be inducers of CYP450 enzymes. Donepezil (a moderate CES2 inhibitor) caused a mild increase (by approximately 20%) of the AUC of E2609 when coadministered with E2609 but not when dosed at least 2 hours apart from E2609. E2609 (which inhibits the P-glycoprotein 1 transporter) did not affect the PK properties of digoxin. Nonclinical studies also indicated that other CYP pathways apart from CYP3A4 would not be major pathways of metabolism of E2609. Therefore, on the basis of drug interaction considerations, the only restriction of concomitant medications is that for strong inhibitors of CYP3A4.

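### The TEAE definition stops at the end of treatment and only TEAEs are tabulated, so AEs and SAEs starting in the 12-week follow-up are listed but not counted

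*Protocol*

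**What the plan says.** Section 9.7.1.8.2 defines the TEAE by its first limb: "A TEAE is defined as an AE that emerges during treatment, having been absent at pretreatment (Baseline"). A second limb covers re-emergence during treatment. The third reads: "Worsens in severity during treatment relative to the pretreatment state, when the AE is continuous". None of the three gives a number of days after the last dose.

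The same section fixes what is tabulated: "Only those AEs that are treatment-emergent will be included in summary tables". Everything else goes to listings: "All AEs, treatment-emergent or otherwise, will be presented in subject data listings". The SAE table follows the rule: "The number (percentage) of subjects with treatment-emergent SAEs will be summarized by MedDRA SOC and preferred term for each treatment group". So does the table of events leading to death.

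Collection runs longer. Under section 9.5.1.5.1, AEs "should be collected beginning from the time the subject signs the study ICF through the last visit (Visit 20"), and SAEs are collected for 3 months after the last dose. Section 9.1.2 splits the Randomization Phase into a 78-week Treatment Period and a Follow-Up Period of 12 weeks after the last dose.

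The primary endpoint in section 9.7.1.1.1 is: "Safety and tolerability, which include incidence of TEAEs and SAEs, laboratory parameters, vital signs, and ECG parameters". SAEs carry no treatment-emergent qualifier there.

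**The concern.** AE and SAE incidence is part of the primary endpoint, and the protocol takes trouble to collect events for 12 weeks after dosing stops. If the tables close at the last dose, an infection, rash or SAE that begins the next day is recorded and listed but counted in no by-group incidence.

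The protocol itself gives reasons to look at this period. On the multiple ascending dose study, section 7.1 reports: "These effects on lymphocyte counts gradually resolved from Day 20 to Day 35, which were 6 and 21 days, respectively, after administration". The count there is from the final dose, on Day 14. The same paragraph says that low counts at 200 and 400 mg could raise the risk of herpes relapse or other infection. Section 9.3.3 follows subjects taken off drug with an infection for 12 weeks or longer. With about 15 subjects per arm, each uncounted subject is visible in a percentage.

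**Working it through.** **Reading the sections together.** Is a post-dose event inside or outside *during treatment*?

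- Section 9.1.2: Treatment Period and Follow-Up Period are distinct, and the second starts after the last dose.
- Section 9.7.1.8.3: the end-of-treatment laboratory value is the last on-treatment one.
- Section 9.7.1.5: concomitant medication is counted up to the date of the last dose.
- Section 9.7.1.8.2: no limb of the definition reaches beyond treatment.

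All four point the same way, and no section at hand extends the AE period. A post-dose onset is therefore not a TEAE and, by the tables rule, is not tabulated.

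**The protocol's own day counts.**

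- Last dose in the multiple-dose study is Day 14: 20 − 14 = 6 days and 35 − 14 = 21 days. Both match section 7.1.
- Collection window here: 78 + 12 = 90 weeks. Day 547 + 84 = Day 631, which matches Visit 20 in Table 7.

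**Share of time from first dose to Visit 20 outside the tables** = 12 / (weeks on drug + 12).

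| Stops at week | Calculation | Share of time |
|---|---|---|
| 78 (completer) | 12/90 | 13.3% |
| 52 | 12/64 | 18.8% |
| 26 | 12/38 | 31.6% |
| 12 | 12/24 | 50.0% |

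These are shares of calendar time. They say nothing about how many events fall there.

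**Weight of one subject.** Section 9.7.2 gives 15 per dose group: 1/15 = 6.7 percentage points.

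**Chance that an arm holds at least one such subject.** The documents give no post-dose event rate, so p below is an assumption. Probability = 1 − (1 − p)^15.

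- p = 5%: 54%
- p = 10%: 79%
- p = 20%: 96%

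This counts subjects with any post-dose event. A subject who already has a TEAE in the same preferred term and system organ class would not change those incidences.

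**Endpoint against table.** Section 9.7.1.1.1 names SAEs; the SAE table in section 9.7.1.8.2 holds treatment-emergent SAEs. An SAE in follow-up fits the endpoint's wording, is collected by design, and enters no table.

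**The case against.** The strongest reply is that the protocol never says when treatment ends for AE attribution, and that a post-dose window is a detail usually set in the SAP, to which section 9.7.1 defers. That would answer mere silence. Here the protocol states both the definition and the tables-only rule and separates Follow-Up from Treatment, so a SAP that added a window would be departing from the natural reading.

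The second reply is that the effect is softened, and this stands. All AEs, SAEs and AEs leading to death are listed, for about 60 subjects. Laboratory tables run by postbaseline visit, so lymphocyte subsets and immunoglobulins in follow-up do reach the by-group tables. The DSMB sees all safety data unblinded about every 3 months. The AE analysis is descriptive.

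A reader might also infer four stronger things that the documents do not support:

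- *That the immune effect persists for weeks at these doses.* The 6 to 21 day recovery followed 14 days of dosing in healthy subjects, with the clearest reductions at 200 and 400 mg and some CD4 reduction at 50 to 100 mg. Section 9.4.4 puts exposure at this trial's top dose below that of 100 mg in that study.
- *That events during a temporary suspension are excluded as written.* Sections 9.4.1 and 9.4.7 place suspensions for concurrent illness and steroid use within the treatment period, and section 9.5.5 separates suspension from discontinuation.
- *That Amendment 04 added follow-up visits because of the multiple-dose data.* The revision history gives closer post-treatment monitoring of immunological changes as the reason and does not cite those data.
- *That the undercount favours the higher doses.* No post-dose event rate by dose is given. Subjects stopped for infection or rash already have an on-treatment event and count once per term and organ class.

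**Conclusion.** The point holds as a defect of definition and should be fixed. Followed as written, AEs and SAEs with onset after the last dose are collected to Visit 20 and only listed, and the SAE table is narrower than the primary endpoint. This rests on reading *during treatment* as ending with the last dose, which sections 9.1.2, 9.7.1.5 and 9.7.1.8.3 support.

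The untabulated time runs from 13% for a completer to 50% for a stop at week 12, and each uncounted subject is worth 6.7 points in an arm of 15. How many events this would drop, and whether they would be uneven across doses, cannot be determined from the protocol. Persistence of the lymphocyte effect here is possible, not shown. Given the listings, the by-visit laboratory tables and DSMB review, this is a correction worth making rather than one that undermines the trial.

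**What to change.** In section 9.7.1.8.2:

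1. State that the treatment-emergent period runs from the first dose through a fixed window after the last dose. Twenty-eight days is one choice: it covers the 21-day recovery and matches the 28 days after last treatment already used for pregnancy reporting in section 9.5.4.2.
2. State, for clarity only, that temporary suspensions fall inside that period.
3. Add a table by treatment group of AEs and SAEs with onset from the end of the window to Visit 20. With a 28-day window this covers the remaining 12 − 4 = 8 weeks. Together the tables then span the full collection period after first dose, and SAE reporting matches the primary endpoint.

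The cost is a change to the definition and one extra table on data already collected. Some reported incidences may be slightly less favourable.
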